Study Duration	
The duration of the enrolment period is estimated to be approximately 28 months.
 
Each patient's participation in the study will last approximately 18 months and will include:
 
 
▪ pre-treatment period (pre-screening and screening, treatment of concurrent diseases) up to 15 days;
 
▪ a treatment period of 1 day;
 
▪ an observation period in hospital of a total of 15 days, including the treatment day (Day 1);
 
▪ an out-patient follow-up period of 18 months with visits at 3, 6, 12 and 18 months.
 
 
The total duration of the study is estimated to be 46 months.

Study Schedule	
D-15 to D-1: pre-screening and screening
 
 
• including the baseline assessment: D-4 to D-1
 
 
D1: treatment day
 
D1 to D15: observation period at hospital
 
D11: initial assessment of treatment effect (lumbar puncture)
 
D15: end-of-hospitalisation visit
 
Out-patient follow-up visits at 3 months, 6 months, 12 months and 18 months

Sample Size Calculation	
The sample size is based on the largest number of patients who can be enrolled within a reasonable timeframe.
 
The sample size will be 155 late-stage patients.
 
Patients lost to follow-up who fled the region due to armed conflict or natural disaster will be replaced. A provision of 5% (7 patients) is planned in order to allow for replacement of patients lost to follow-up. Thus, a total of 162 patients will be included.
 
As a result of the reduction in the number of patients, it is estimated that approximately 50 early- or intermediate-stage patients may be enrolled in the study during the enrolment period.

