### **9.1. Sample Size Determination**

The sample size is based on the largest number of patients who can be enrolled within a reasonable timeframe. It is expected that 155 late-stage patients should be enrolled within approximately 2 years. A provision of 5% (7 patients) is planned in order to allow for replacement of patients lost to follow-up who fled the region due to armed conflict or natural disaster. Approximately 50 early- and intermediate-stage patients could be enrolled within this timeframe. As a reminder, enrolment of early- and intermediate-stage patients will begin approximately 6 months after the start of enrolment of late-stage patients and will end at the same time.

If the observed success rate is around 89% (the same as the expected rate for fexinidazole and the observed rate with eflornithine) then the width of the 95% Jeffreys confidence interval will be 9.8% (83.4%–93.2%) for an 89% success rate. The width decreases with an increase in the success rate to reach 7.4% (89.7%–97.1%) for a 94% success rate. In contrast, the precision is not highly sensitive to the sample size. With 200 patients, the width of the confidence interval is 8.7% (84.1%–92.8%) for an 89% success rate. Indeed, the sample size must increase by 50%, i.e. 300 patients instead of 200, to reduce the width of the lower arm of the 95% confidence interval by one percentage point.

In early- and intermediate-stage patients, the expected success rate is around 91%, i.e. the same as for pentamidine. The width of the confidence interval with 50 patients will be of the order of 17%.

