## 9.8. Handling of Missing Data and Patients Lost to Follow-up

The primary endpoint is the outcome at 18 months. If outcome assessed at the final visit is missing, the **primary imputation method** will consist in imputing a probable success (considered as a success) to patients who attended the 18-month visit, but who refused the lumbar puncture planned at the visit, who showed no signs or symptoms of HAT at 18 months, who did not subsequently report any symptoms of relapse and for whom the outcome was considered as favourable at the last available assessment (17). If these criteria are not fulfilled, the patients will be considered as treatment failures. The outcome for patients who did not attend the 18-month visit or later will also be considered as a failure, except for patients who fled the region due to armed conflict or natural disaster.

Because the historical data may not allow for other imputation methods to be applied, only the primary imputation method will be used. The method will be described in detail in the SAP. Sensitivity analyses will be performed to assess the impact of missing data on acoziborole. The method will be described in detail in the SAP.

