### 7.2. Type I error

For all analyses, the type I error ( $\alpha$ ) is set to 0.05, two sided.

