#### Best case method (for sensitivity analysis):

The algorithm defined in [Section 10](#) will be used to derive the outcome at 18, 12 and 6 months, with the following changes. The following patients will be considered as **success**:

- Patients lost to follow-up (prior or at visit 18, 12 and 6 months, respectively)
- Patients who refused all post treatment lumbar punctures

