#### Observed case method (for sensitivity analysis):

The algorithm defined in [Section 10](#) will be used to derive the outcome at 18, 12 and 6 months, with the following changes. The following patients will be considered as having a **missing** outcome:

- Patients with missing data at visit 18, 12 and 6 months, respectively.

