Note: it could be difficult to get all individual historical data of all available studies using NECT. In other words, it will be difficult to use exactly the same criteria for determining the status of each patient treated with NECT. The figures presented in Table 4 and especially the overall estimate will be used as a yardstick even if they are more liberal (except for the Mesu's study) than what could be obtained from the strict application of algorithm. As an example, in Priotto's study (2009) 129 patients completed the M18 visit and were proven cured (i.e. WBC in CSF < 20). This represents a success rate of 88.8%. 138 patients out of 143 were considered as cured by the authors leading to a success rate of 96.5%. All deaths regardless the cause (5), relapses (2) and absence of any post-treatment assessment (1) were considered as failure in Table 4 leading to a failure rate of 5.6% (S.R. = 94.4%). Lost to follow-up due to moved out (2 patients moved out) and absence of assessment (probably lumbar puncture) at M18 (4 patients) are not counted as failures in Table 4 and this sort of decision is a potential source of bias (overestimation of success rate of NECT compared to the strict application of the algorithm). Because the retained result in Table 4 is rather in favour of NECT, the possible bias is in disfavour of acoziborole when the yardstick (NECT) is compared to acoziborole.

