
| Derivation algorithm for stage 1 and intermediate stage (month 18)   | Derivation algorithm for stage 2 (Month 18)  |
|--|--|
| 
Earlier (before M18) unfavorable outcome: increase of WBC in CSF at M6 or M12 with respect to EOH
 
⇒ YES ⇒ 9: Failure (stop)
 
↓
 
NO (no information or no earlier unfavorable assessment)
 
↓
 
Patient has clinical signs or symptoms at M18 evoking a failure
 
⇒ YES ⇒ 10: Failure (stop)
 
↓
 
NO (no clinical signs or symptoms evoking a relapse at M18)
 
↓
 
WBC in CSF ≤ 20 at M12 or absence of LP at M12 and for both cases no increase WBC in CSF at M6 with respect to EOH and no sign and symptoms at M18 evoking a relapse:
 
⇒ YES ⇒ 11: Success (stop) [b]
 
↓
 
NO (at least one criterion not met)
 
↓
 
Patient refused all post treatment lumbar punctures
 
⇒ YES ⇒ 12: Failure (stop) [a,b]
 
↓
 
All other cases ⇒ 13. Failure
 | 
Earlier (before M18) unfavorable outcome: WBC in CSF > 50 at M6 or WBC in CSF > 20 at M12 or increasing between M6 and M12
 
⇒ YES ⇒ 9: Failure (stop)
 
↓
 
NO (no information or no earlier unfavorable assessment)
 
↓
 
Patient has clinical signs or symptoms at M18 evoking a failure
 
⇒ YES ⇒ 10: Failure (stop)
 
↓
 
NO (no clinical signs or symptoms evoking a relapse at M18)
 
↓
 
WBC in CSF ≤ 20 at M12 or in absence of LP at M12 and for both cases WBC in CSF ≤ 50 at M6 and no signs and symptoms at M18 evoking a relapse:
 
⇒ YES ⇒ 11: Success (Stop) [b]
 
↓
 
NO (at least one criterion not met)
 
↓
 
Patient refused all post treatment lumbar punctures
 
⇒ YES ⇒ 12: Failure (Stop) [a,b]
 
↓
 
All other cases ⇒ 13. Failure
 |

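### No planned sensitivity analysis counts the presumed cures of SAP 10.1, stage 2 box 11, as failures, so the success rate has no lower bound for them

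*SAP*

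**What the plan says.** SAP 10.1 derives the month-18 outcome through numbered boxes. For stage 2:

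- Boxes 1 to 4 make death, rescue medication, trypanosomes and loss to follow-up failures.
- Boxes 5 to 8 use a reliable CSF white-cell count at month 18 or, failing that, later. Boxes 6 and 8 are the successes (count of at most 20).
- Boxes 9 and 10 apply when there is no such count. An unfavourable earlier count, or signs at month 18, gives failure.
- Box 11 then gives success if the month-12 count is at most 20 or "in absence of LP at M12 and for both cases WBC in CSF ≤ 50 at M6 and no signs and symptoms at M18". It carries only the flag that triggers resampling in the fair case.
- Boxes 12 (all post-treatment punctures refused) and 13 (everything else) are failures.

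Protocol 9.8 says "Sensitivity analyses will be performed to assess the impact of missing data on acoziborole" and leaves the method to the SAP. SAP 8.6.1.2 lists six analyses: per protocol, Evaluable, Treated, fair case, best case and observed case. Under SAP 7.6.1 the fair case redraws responses at random from the non-missing ones. The best case turns into successes the patients lost to follow-up and "Patients who refused all post treatment lumbar punctures". The observed case sets to missing the outcome of "Patients with missing data at visit 18, 12 and 6 months, respectively".

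Protocol 2.2.1 allows a probable cure for a patient who refuses the final puncture. It requires no suggestive signs and a CSF count of at most 20 at the last available assessment, at 6 months or later.

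**The concern.** Protocol 9.6.2 and SAP 8.7 set no objective rule for success. The observed rate and the lower end of its 95% interval are to be weighed against historical NECT results. Box 11 is the place where the primary algorithm resolves a missing month-18 CSF result in favour of acoziborole. If the planned analyses never reverse that choice, the report cannot show how far the lower limit depends on presumed rather than demonstrated cures. The point weighs more if box 11 admits patients whom the Protocol's own probable-cure condition would not.

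**Working it through.** **How each analysis treats the relevant boxes**

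| Analysis | Box 11 | Boxes 4 and 12 |
|---|---|---|
| Primary (mITT) | success | failure |
| #1 Per protocol | success | failure |
| #2 Evaluable | success | excluded |
| #3 Treated | success | failure; patients who fled are added as failures |
| #4 Fair case | resampled | resampled |
| #5 Best case | success | success |
| #6 Observed case | missing | missing |

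No row has failure under box 11.

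**Reproducing the plan's intervals.** "The sample size will be 155 late-stage patients" (Protocol Summary), and alpha "is set to 0.05, two sided" (SAP 7.2). The Jeffreys limits are the 2.5% and 97.5% quantiles of Beta(x + 0.5, n − x + 0.5). For 138/155 this gives 83.4–93.2, which agrees with Protocol 9.1: "the width of the 95% Jeffreys confidence interval will be 9.8% (83.4%–93.2%) for an 89% success rate". For 146/155 it gives 89.7–97.1, also as stated there for 94%.

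**Number of box 11 patients (B).** The documents give none, so B is an assumption. SAP 8.6.1.3 describes a 2009 randomised NECT trial of 143 patients. Four patients without a month-18 assessment, and two who had moved away, were not counted as failures.

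- 4/143 = 2.8%; × 155 = 4.3
- 6/143 = 4.2%; × 155 = 6.5

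This gives about 4 to 7 of 155. The upper end is generous, because patients lost after moving would be box 4 failures here.

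**Effect on the rate.** Take S = 146 primary successes, N = 155, and L of the 9 failures in boxes 4 and 12.

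- Fair case (expected) and observed case: (S − B)/(N − B − L)
- Box 11 counted as failure: (S − B)/N

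| B | Primary | Fair/observed, L = 0 | Fair/observed, L = 4 | Box 11 as failure |
|---|---|---|---|---|
| 4 | 94.2% (89.7–97.1) | 142/151 = 94.0% | 142/147 = 96.6% | 142/155 = 91.6% (86.5–95.2) |
| 7 | 94.2% (89.7–97.1) | 139/148 = 93.9% | 139/144 = 96.5% | 139/155 = 89.7% (84.2–93.7) |

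The fair and observed cases exceed the primary rate as soon as L > B(N − S)/S. That threshold is 4 × 9/146 = 0.25 for B = 4 and 7 × 9/146 = 0.43 for B = 7. A single lost or never-punctured patient among the 9 failures is enough. With L = 4 the best case is 150/155 = 96.8%.

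Each recoded patient costs 1/155 = 0.65 points. The lower limit falls by 89.7 − 86.5 = 3.2 points (B = 4) or 89.7 − 84.2 = 5.5 points (B = 7). The planned distance from estimate to lower limit is 94.2 − 89.7 = 4.5 points.

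**The two definitions.** Take, for illustration, a stage 2 patient with a month-6 count of 35, no later puncture and no signs at month 18. Box 9 does not apply (35 is not above 50), nor does box 10, so box 11 gives success. Under Protocol 2.2.1 the last available count is above 20, so the probable-cure condition is not met. Protocol 9.8 makes a patient who does not meet its criteria for imputed success a failure. Protocol Table 1 classes a month-6 count between 20 and 50 as uncertain. SAP 11 does not list this among the changes from the Protocol.

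**The NECT comparator.** SAP 8.6.1.3 says that "129 patients completed the M18 visit and were proven cured" and gives this as 88.8%. But 129/143 = 90.2%, whereas 127/143 = 88.8%.

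**The case against.** A reader might infer that nobody without a month-18 CSF result is ever counted as a failure, or that the sensitivity set leans only one way. The documents do not support that. Boxes 4, 12 and 13 are failures in the primary analysis and stay so in #1 and #3, and the Treated set adds patients who fled as failures.

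A reader might also infer that box 11 is never varied. It is. The fair case replaces a certain success by a draw from a pool that contains failures, and the observed case removes the patient. What remains is that both effects are small, assume missingness at random, and are easily masked because the same step resamples or drops failures in boxes 4 and 12.

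It is tempting to take 138 − 129 = 9 of 143 from the NECT trial as the share of presumed cures. Three of those nine are deaths excluded by that trial's authors and two are patients who moved. Neither group is comparable with box 11.

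Other objections stand in part:

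- Planned outputs already count month-18 punctures (SAP 8.1) and list individual outcomes (SAP 9.1.9, listing 16.2.7), so a careful reader could roughly bound the number of presumed cures.
- Protocol 9.8 does not promise a worst case, and probable cure is part of the Protocol's primary endpoint.
- The Protocol is not uniform: the month-18 row of Table 1 accepts a symptom-free refuser as favourable without any count condition.
- Treating a patient with a month-12 count of at most 20 and no signs as a failure is deliberately extreme. That argues against changing the primary analysis, not against reporting the bound.

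**Conclusion.** The point holds in this limited form. Box 11 successes are varied only by resampling or deletion. The plan has a best case but no analysis that counts them as failures, so it gives no lower bound for presumed cures. If 4 to 7 of 155 patients reach box 11 and the primary result is 146/155, the estimate would fall by 2.6 to 4.5 points and the lower limit by 3.2 to 5.5. The 4 to 7 is scaled from a single historical trial, and SAP 8.6.1.3 itself says only that a missing puncture is the probable reason for the four unassessed patients. If few patients reach box 11, the effect is negligible, and reporting the count would show that.

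Separately, box 11 and Protocol 2.2.1 disagree on which earlier count supports a presumed cure. The passages must be reconciled; the documents do not settle which should prevail. None of this makes the primary analysis invalid. It is a cheap improvement to a study read on its rate and lower limit.

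**What to change.** 1. Add sensitivity analysis #7, proven cure, to SAP 7.6.1, 8.6.1.2 and the output list under 14.2.1.2. Success comes only through boxes 6 and 8, and box 11 counts as failure. Run it for stage 2 on the mITT and Treated sets with the Jeffreys interval.
2. Report the number of stage 2 patients in box 11.
3. Reconcile box 11 with Protocol 2.2.1 and 9.8, and record any intended difference in SAP 11. Also align the fair-case text, which spares patients with proven success at another visit, with the flag that resamples every box 11 patient.
4. Quote the NECT proven-cure figure beside the new result only after 129 of 143 and 88.8% have been reconciled. The SAP gives no such count for the other yardstick studies, so their looser definitions should be stated alongside.

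The cost is one derivation flag, one additional output and a short text correction. The primary analysis is unchanged. The downside is one additional, less favourable figure in the report.

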**For sensitivity analyses:**

[a] will be considered as a success with the best case method (see [Section 7.6.1](#)).

[b] re-sampling will be applied with the fair case method (see [Section 7.6.1](#)).

## 10.2. Outcome at 12 months

Note: this algorithm will be used in the time course of the response: status at M12.

| Derivation algorithm at 12 months for stage 1 and intermediate stage  | Derivation algorithm at 12 months for stage 2  |
|---|--|
| Patient is $\Rightarrow$ 1: Dead (any reason of death and any time between drug intake and M12) $\Rightarrow$ (definitive) | Patient is $\Rightarrow$ 1: Dead (any reason of death and any time between drug intake and M12) $\Rightarrow$ (definitive)                                      |
| Failure (stop)   | Failure (stop)  |
| $\Downarrow$  | $\Downarrow$   |
| Alive   | Alive  |
| $\Downarrow$  | $\Downarrow$   |
| Patient requires rescue medication for HAT at M12 or before  | Patient requires rescue medication for HAT at M12 or before   |
| $\Rightarrow$ YES $\Rightarrow$ 2: Failure (stop)  | $\Rightarrow$ YES $\Rightarrow$ 2: Failure (stop)   |
| $\Downarrow$  | $\Downarrow$   |
| NO rescue medication so far   | NO rescue medication so far  |
| $\Downarrow$  | $\Downarrow$   |
| Evidence of trypanosomes in any body fluid at M12 or between drug intake and M12 visit                                     | Evidence of trypanosomes in any body fluid at M12 or between drug intake and M12 visit  |
| $\Rightarrow$ YES $\Rightarrow$ 3: (definitive) Failure (stop)   | $\Rightarrow$ YES $\Rightarrow$ 3: (definitive) Failure (stop)  |
| $\Downarrow$  | $\Downarrow$   |
| NO observed trypanosomes so far   | NO observed trypanosomes so far  |
| $\Downarrow$  | $\Downarrow$   |
| Patient Lost to follow-up at 12M (no survival information at M12 and later)  | Patient Lost to follow-up at 12M (no survival information at M12 and later)   |
| $\Rightarrow$ YES $\Rightarrow$ 4: Failure (Stop) [a,b]  | $\Rightarrow$ YES $\Rightarrow$ 4: Failure (Stop) [a,b]   |
| $\Downarrow$  | $\Downarrow$   |
| NO (the patient is not lost to follow-up)   | NO (the patient is not lost to follow-up)  |
| $\Downarrow$  | $\Downarrow$   |
| Non-hemorrhagic lumbar puncture at M12 and WBC in CSF >20 cells   | Non-hemorrhagic lumbar puncture at M12 and WBC in CSF at M12 <math>\geq</math> 50 cells   |
| $\Rightarrow$ YES $\Rightarrow$ 5: Failure (stop)  | $\Rightarrow$ YES $\Rightarrow$ 5: Failure (stop)   |
| $\Downarrow$  | $\Downarrow$   |
| NO (WBC in CSF at M12 $\leq$ 20 cells or no reliable count of WBC in CSF at M12)  | NO (WBC in CSF at M12 $<$ 50 cells or no reliable count of WBC in CSF at M12)  |
| $\Downarrow$  | $\Downarrow$   |
| Non-hemorrhagic lumbar puncture at M12 and WBC in CSF at M12 <math>\leq</math> 20 cells                                    | Non-hemorrhagic lumbar puncture at M12 with WBC in CSF < 50 but > 20 and increase of WBC in CSF with respect to M6 or sign and symptoms evoking a failure |
| $\Rightarrow$ YES $\Rightarrow$ 6: Success (Stop)  | $\Rightarrow$ YES $\Rightarrow$ 6: Failure (stop)   |
| $\Downarrow$  | $\Downarrow$   |
| NO (no reliable count of WBC in CSF at M12)   | NO (patient did not meet at least one of the previous criteria at M12)   |
| $\Downarrow$  | $\Downarrow$   |

| Derivation algorithm at 12 months for stage 1 and intermediate stage  | Derivation algorithm at 12 months for stage 2   |
|---|---|
| 
No lumbar puncture at M12 or no reliable count of WBC in CSF at M12 but reliable number of WBC in CSF reported later (M18 or other additional visit)
 
⇒ YES ⇒ WBC in CSF > 20 ⇒ 7: Failure (Stop)
 
⇒ YES ⇒ WBC in CSF ≤ 20 and no signs or symptoms evoking a relapse ⇒ 8: Success (Stop)
 
↓
 
NO (no later reliable count of WBC in CSF)
 
↓
 
No reliable WBC count in CSF at M12 and later and Failure at M18 for any reason
 
⇒ YES ⇒ 9: Failure at M12 (Stop)
 
↓
 
NO
 
↓
 
No reliable count of WBC in CSF at M18 and M12 but WBC counts at M6 available and no signs and symptoms evoking a failure at M12 or M18
 
⇒ YES ⇒ WBC in CSF at M6 ≤ 5 and smaller than WBC in CSF at EOH ⇒ 10: Success (stop) [b]
 
⇒ NO ⇒ WBC in CSF at M6 > 5 or larger than WBC in CSF at EOH ⇒ 11: Failure (stop)
 
↓
 
NO (no lumbar puncture at M6, M12 and M18)
 
↓
 
Patient refused all post-treatment lumbar punctures but was met at M24 or later with no signs and symptoms evoking a relapse (normal activity)
 
⇒ YES ⇒ 12: Success at M12 [b]
 
↓
 
NO (Patient not met at M24 or later)
 
↓
 
Patient refused all post treatment lumbar punctures ⇒ YES ⇒ 13: Failure (Stop) [a,b]
 | 
No lumbar puncture at M12 or no reliable count of WBC in CSF at M12 but reliable number of WBC in CSF reported later (M18 or other additional visit)
 
⇒ YES ⇒ WBC in CSF > 20 ⇒ 8: Failure (Stop)
 
⇒ YES ⇒ WBC in CSF ≤ 20 ⇒ 9: Success (Stop)
 
↓
 
NO (no later reliable count of WBC in CSF)
 
↓
 
No reliable WBC count in CSF at M12 and later and Failure at M18 for any reason
 
⇒ YES ⇒ 10: Failure at M12 (Stop)
 
↓
 
NO
 
↓
 
No reliable count of WBC in CSF at M18 and M12 but WBC counts at M6 available and no sign and symptoms evoking relapse at M12 or M18
 
YES ⇒ WBC in CSF at M6 ≤ 20 cells ⇒ 11: Success (stop) [b]
 
NO ⇒ WBC in CSF at M6 > 20 cells ⇒ 12: Failure
 
↓
 
NO (no lumbar puncture at M6, M12 and M18)
 
↓
 
Patient refused all post-treatment lumbar punctures but was met at M24 or later with no signs and symptoms evoking a relapse (normal activity)
 
⇒ YES ⇒ 13: Success at M12 [b]
 
↓
 
NO (Patient not met at M24 or later)
 
↓
 
Patient refused all post treatment lumbar punctures ⇒ YES ⇒ 14: Failure (Stop) [a,b]
 |

For sensitivity analyses:

[a] will be considered as a success with the best case method (see [Section 7.6.1](#)).

[b] re-sampling will be applied with the fair case method (see [Section 7.6.1](#)).

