##### **Endpoints in Patients with Early- or Intermediate-stage HAT**

Two efficacy endpoints will be used for patients with early- and intermediate-stage HAT: the outcome at 12 months and the outcome at 18 months after receiving treatment. A patient will be considered as a success at 12 months if the patient is alive with no evidence of trypanosomes in any body fluid and if the CSF

WBC is equal to or less than 20/ $\mu$ L. A patient with no parasitological evidence of relapse, but with a CSF WBC above 20/ $\mu$ L or who, in the Investigator's opinion, requires rescue treatment, will be considered as a relapse. A patient who refuses the lumbar puncture at 12 months will be classified as a probable cure (success) in the absence of any clinical signs or symptoms suggestive of THA or with another obvious aetiology, provided that the outcome was favourable, i.e. a CSF WBC equal to or less than 5/ $\mu$ L, at 6 months. Death for any reason, patients lost to follow-up and not retrieved or patients with no post-treatment lumbar puncture will be considered as failures, with the exception of patients who fled the region due to armed conflict or natural disaster. For memory, patients who fled the region due to armed conflict or natural disaster will not be included in the mITT population and will therefore not be taken into account in the calculation of the success rate. A patient with early- or intermediate-stage HAT will be considered as a **success** at 18 months if the CSF WBC is equal to or below 20/ $\mu$ L and in the absence of trypanosomes, rescue treatment and signs or symptoms suggestive of a relapse. If the patient does not have a lumbar puncture at 18 months, the outcome at 6 months or at 12 months will be used.

A patient with early- or intermediate-stage HAT will be considered as a success at 6 months and at 12 months if the CSF WBC is equal to or less than 20/ $\mu$ L and in the absence of trypanosomes, rescue treatment and signs or symptoms suggestive of a relapse. If the patient does not have a lumbar puncture at 6 months, the outcome at 12 months and, if necessary, at 18 months will be used. If the patient does not have a lumbar puncture at 12 months, the outcome at 18 months will be used and, if necessary, the outcome at 6 months will be used. If no post-treatment lumbar punctures were performed, the outcome will be considered as unfavourable.

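### Early- and intermediate-stage patients with no reliable CSF count after month 6: the protocol gives two 12-month rules, and the SAP can call one CSF result a success at 6, a failure at 12 and a success at 18 months

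*SAP*

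**What the plan says.** **Protocol 2.2.2, early- and intermediate-stage endpoints.** The 12-month outcome is one of two efficacy endpoints for this cohort. The first paragraph makes a patient who refuses the 12-month puncture a probable cure, absent suggestive signs, "provided that the outcome was favourable, i.e. a CSF WBC equal to or less than 5" per µL at 6 months. The second paragraph says a patient is "considered as a success at 6 months and at 12 months if the CSF WBC is equal to or less than 20/ $\mu$ L". For a missing 12-month puncture it adds that "the outcome at 18 months will be used and, if necessary, the outcome at 6 months will be used". For a missing 18-month puncture, the first paragraph says "the outcome at 6 months or at 12 months will be used".

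**SAP Section 10, stage 1 and intermediate column.** These are the boxes that decide when there is no reliable count at month 12 or later:

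- 10.3 (month 6), box 5: success if the count is ≤20 and below EOH, with no signs. Box 7 makes everyone remaining a failure.
- 10.2 (month 12), box 9: failure if "No reliable WBC count in CSF at M12 and later and Failure at M18 for any reason". Box 10: success if "WBC in CSF at M6 ≤ 5 and smaller than WBC in CSF at EOH". Box 11: failure if the month-6 count is above 5 or larger than at EOH. Boxes 12 and 13 cover only patients who refused every post-treatment puncture. There is no residual box.
- 10.1 (month 18), box 9: failure if the count rose from EOH at month 6 or 12. Box 11: success if, with no month-12 puncture, there was "no increase WBC in CSF at M6 with respect to EOH" and no signs at month 18. Box 13 makes everyone remaining a failure.

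SAP Section 11, which lists departures from the protocol, does not mention any of these rules.

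**The concern.** Three visits use the month-6 count in three different ways: ≤20 with a fall (10.3), ≤5 with a fall (10.2), and no rise with no upper limit (10.1). When no later count exists, the classification should not change direction, because no new CSF information has arrived. Under these rules it can.

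The 12-month success rate in this cohort is reported with a Jeffreys interval. SAP 8.6.3 also feeds the 6-, 12- and 18-month outcomes into a logistic mixed model that reports odds ratios and p-values for 12 versus 6 and 18 versus 12 months. A dip at month 12 made by the derivation rule would appear there as a change over time. The programmer must also choose between two protocol rules without being told which one the SAP implements.

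**Working it through.** **Inputs.** The rules above, and about 50 planned patients (Protocol 9.1). The patient traced is alive, not rescued, trypanosome-free, without signs, seen at month 18, with a month-6 count and no reliable count at month 12, month 18 or later.

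**Step 1: the protocol's two rules.** Suppose this patient refused the 12-month puncture and had 10 cells at month 6. The first paragraph does not allow a probable cure, because 10 > 5. The second carries the month-6 outcome, a success because 10 ≤ 20. The rules collide for refusers with 6 to 20 cells at month 6 and no later puncture.

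**Step 2: trace through the SAP and the two protocol rules.** Box numbers are in brackets.

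| EOH, M6 | SAP M6 | SAP M12 | SAP M18 | Protocol, limit 5 | Protocol, limit 20 |
|---|---|---|---|---|---|
| 12, 10 | success (5) | failure (11) | success (11) | not a cure | success |
| 10, 5 | success (5) | success (10) | success (11) | cure | success |
| 3, 3 | failure (7) | neither 10 nor 11 | success (11) | cure | success |
| 20, 20 | failure (7) | failure (11) | success (11) | not a cure | success |
| 5, 8 | failure (7) | failure (9) | failure (9) | not a cure | success |
| 40, 30 | failure (6) | failure (11) | success (11) | not a cure | failure |

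The first row reverses twice on one CSF result. The third is a tie: box 10 needs a smaller count, and box 11 needs a count above 5 or a larger one. The last row shows that 10.1 box 11 sets no upper limit at month 6.

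**Step 3: how general this is.** Take all EOH and month-6 counts from 0 to 20. Every pair with month-6 count s from 6 to 20 and EOH at least s is a 12-month failure and an 18-month success: the sum of (21 − s) over s = 6,…,20 is 15 + 14 + … + 1 = 120 pairs. Of these, the 15 ties are also failures at month 6; the other 105 run success, failure, success. The six ties from 0 to 5 fit neither box 10 nor box 11 at month 12. These are counts of combinations, not expected numbers of patients.

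**Step 4: size.** The plan's stated interval width of about 17 points for 50 patients is matched by 45/50 (79.5% to 96.1%, 16.6 points). Each reclassified patient moves the rate by 1/50 = 2.0 points:

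- 46/50 = 92% (82.1% to 97.2%)
- 45/50 = 90% (79.5% to 96.1%)
- 44/50 = 88% (76.9% to 94.8%)

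**The case against.** **The limit of 5 has a source.** SAP 10.2 carries out the protocol's explicit refusal rule. A reader might infer that 5 is an SAP mistake and 20 is the intended rule; the documents do not support this, because both limits stand in Protocol 2.2.2. What has no source there is the comparison with EOH.

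**The protocol conflict is narrow.** The first rule concerns refusal, the second any missing puncture. The first also implies, without stating it, that a refuser above 5 cells is a failure. Both points stand, and they limit the conflict to the refusers in Step 1.

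**The tie may have a class.** Boxes 10 and 11 carry YES and NO labels, and a programmer who follows the labels would send 3 and 3 to failure. The box text leaves the tie unassigned. This is an ambiguity, not a certain gap, but either reading disagrees with success at month 18.

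**Sensitivity analyses exist.** SAP 8.6.2 applies them to this cohort. The observed-case method sets these 12-month outcomes to missing. Whether the fair-case method resamples them is unclear: its text could cover them, but box 11 lacks the resampling mark. The best-case method does not relabel box 11. They help a reader gauge the effect but do not correct the main estimate or the time-course model.

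**It is a secondary, estimation-only analysis** with no success rule. That stands and limits the severity.

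**Conclusion.** The rules are wrong as written for a secondary endpoint in the early- and intermediate-stage cohort. The protocol's two paragraphs conflict for a definable group, and the SAP's three algorithms give contradictory classes on one CSF result, with nothing in Section 11 to explain it.

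The size is 2 points on the 12-month rate per affected patient if the cohort is about 50. A reader might infer that everyone without a 12-month puncture is affected. The SAP contradiction at 12 versus 18 months needs all the conditions in the working, plus a month-6 count either above 5 and not above EOH, or tied with EOH at 5 or below. A patient lost to follow-up at month 18 with no reliable count from month 12 on is a failure at both visits, so shows no such contradiction. A reader might also suppose that ties are common, or that intermediate-stage patients are hit most; the documents give no figure for either, nor for the number affected.

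**What to change.** 1. Reconcile the two paragraphs of Protocol 2.2.2 into one rule for using the month-6 count when no reliable count exists at month 12 or later. The sponsor must choose the limit.
2. Apply that rule, with the same limit and the same handling of the EOH comparison and of ties, in the stage 1 and intermediate column of SAP 10.1 (boxes 9 and 11), 10.2 (boxes 9 to 11) and 10.3 (box 5). Changing only 10.2 boxes 10 and 11 is not enough. The 3 and 3 patient would still fail at month 6, and the 5 and 8 patient would still fail at month 12, because 10.1 box 9 feeds 10.2 box 9.
3. Add a residual box to 10.2.
4. List the choice in SAP Section 11, and report the 12-month rate under the other limit as a sensitivity analysis.

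The cost is a protocol clarification, SAP wording, small changes to three derivations with their validation, and one extra table. No new data are needed. It should be settled before database lock.
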